7.1.2. Schedule of Study Procedures

Table 1: Schedule of Study Procedures

			Double-Blind Treatment Period (Weeks) ^b									Double-Blind Extension
	Screening	Day 1 ^a	3 ^c	6 ^d	12	18	24	30	36	42 ^c	48/ ET/ EOS/EOT	Every 3 months
Visit Window (+/-)	-28 to -14 days		±1 wk	±1 wk	±1 wk	±1 wk	±1 wk	±1 wk	±1 wk	±1 wk	±1 wk	±2 wks
Fast ≥8 h Prior to Visit ^e	X	X	X	X	X	X	X	X	X	X	X	X
Informed Consent	X											
Medical/PBC History	X											
Inclusion/Exclusion Criteria	X	X										
Physical Exam ^f	X	X		X	X	X	X	X	X		X	X
Vital Signs and Weight	X	X		X	X	X	X	X	X		X	X
Medical and Surgical Procedures		X	X	X	X	X	X	X	X	X	X	X
Adverse Events	X	X	X	X	X	X	X	X	X	X	X	X
Prior and Concomitant Medications	X	X	X	X	X	X	X	X	X	X	X	X
Assessments for Child-Pugh Score ^g	X	X		X	X	X	X	X	X		X	X
Patient Questionnaires (Pruritus VAS, PBC-40, EQ- 5D-5L, and CLDQ) ^h		X		X	X	X	X	X	X		X	X
Randomization/Treatment Assigned		X										
Dispense IP ⁱ		X			X	X	X	X	X	X	X	X
Dose Titration Assessment ^j					X	X	X	X	X	X	X	X
IP Accountability/ Compliance			X	X	X	X	X	X	X	X	X	X

Table 1: Schedule of Study Procedures (Continued)

			Double-Blind Treatment Period (Weeks) ^b									Double-Blind Extension
	Screening	Day 1 ^a	3 ^c	6 ^d	12	18	24	30	36	42 ^c	48/ ET/ EOS/EOT	Every 3 months
Visit Window (+/-)	-28 to -14 days		±1 wk	±1 wk	±1 wk	±1 wk	±1 wk	±1 wk	±1 wk	±1 wk	±1 wk	±2 wks
Urinalysis	X	X									X	X ^p
Urine-based β-hCG Pregnancy Test ^k	X	X		X	X	X	X	X	X		X	X
Virology (HCV/HBsAg)	X											
Serum Chemistry/Hematology/Coagulation ^l	X	X	X	X	X	X	X	X	X	X	X	X
Amylase and Lipase	Sample to be collected if the patient experiences acute pancreatitis or cholecystitis.											
PK Fasting Collection		X		X					X			
PK Serial Collection ^m					X	X	X	X			X	
PD Markers: Bile Acid/C4/FGF-19		X		X	X	X	X	X	X		X	
TE/ELF (HA, P3NP, and TIMP-1) ⁿ		X			X		X		X		X	X ^o
12-Lead Electrocardiogram	X										X	X ^p
Hepatic Ultrasound ^q	X ^r	X ^s					X				X	X ^o
Gallbladder assessment (ultrasound)	X ^r	X ^s										

AE = adverse event; eCRF = electronic case report form; C4 = 7α hydroxy-4-cholesten-3-one; CLDQ = Chronic Liver Disease Questionnaire; ELF = enhanced liver fibrosis; ET = Early Termination; EOS = End of study; EOT = End of Treatment; ; FGF-19 = fibroblast growth factor-19; HA = hyaluronic acid; HCV = Hepatitis C virus; IP = Investigational Product; P3NP = procollagen 3 N-terminal peptide; PBC = primary biliary cirrhosis; PK = pharmacokinetics; TE = transient elastography; wk(s) = week(s), TIMP-1 = tissue inhibitor of metalloproteinase ; VAS = Visual Analogue Scale.

^a Visit schedule should be based on Day 1. Day 1 visit must occur at least 2 weeks after screening visit.

^b Patients should be contacted by telephone/email every 3 weeks (±1 week) between clinic visits starting at Week 9 and continuing to Week 48 to assess for AEs, concomitant medications, medical/surgical procedures, and verify that s/he is dosing as directed. (see Section 9.7.8).

^c Preferably, the patient comes in to the clinic for this visit. Alternatively, site will telephone the patient for assessments and a home health nurse will visit to draw safety labs.

^d Visit should occur 3, 4, or 5 days after taking the Week 6 dose.

- ^e The patient should be instructed to fast overnight (at least 8 hours) prior to each visit. Fasting is required prior to all study visits, including screening, but water is permitted.
- ^f Height and assessment of smoking and alcohol consumption history and current habits will be assessed at Screening and Week 48. Assessment of smoking and alcohol consumption history and current habits will be assessed quarterly after Week 48.
- ^g Child-Pugh Score will be calculated based on ascites assessment, hepatic encephalopathy grade, and central laboratory evaluations per the Child-Pugh scoring system noted in the eCRF.
- ^h The EQ-5D-5L Quality of Life questionnaire is validated for use in multiple languages. If a validated translation is not available in the local language required for a specific study patient, the questionnaire will not be collected. The CLDQ measures change over time in patients with chronic liver disease.
- ⁱ New investigational product bottles will be dispensed if the patient is up-titrated. Unless up-titrated, patients are expected to use up each investigational product bottle before a new bottle will be dispensed. No new bottles will be dispensed if dose frequency is changed. Patients will be instructed to begin dosing on Day 1, after completing all study assessments. Patients will be instructed to take investigational product at approximately the same time of day. Patients must be instructed to swallow the tablet whole; they must not chew, divide, or crush the tablet.
- ^j Dose titration of investigational product may occur starting after the Week 12 Visit, or any study visit thereafter for patients on all dosing regimens, based on tolerability and safety laboratory tests from the previous visit. Subsequent dose titration(s) may occur no earlier than 6 weeks after the previous dose titration and will be based on tolerability.
- ^k Urine β -hCG pregnancy tests must be performed in females of childbearing potential prior to entry and at every visit (except Week 3). If positive, a confirmatory blood test must be performed at the central laboratory. If the confirmatory blood test is also positive, the patient may not continue in the study. (Additional testing may be conducted where required, regionally).
- ^l MELD values will be calculated based on serum chemistry and coagulation values at each visit.
- ^m The patient will be given the option to return to the clinic the following morning for the 24-hour postdose PK sample or samples can be obtained by a home health care designee. Patients who are discontinued from investigational product prior to completion of the study are encouraged to continue to follow the regular visit schedule, with the exception of PK sampling.
- ⁿ The noninvasive radiological liver fibrosis measurement devices (such as, FibroScan[®] device [Echosens; Paris, France]) will be used at all study sites to collect hepatic stiffness measurements.
- ^o Patients will complete a TE/ELF and ultrasound assessment, every 6 months (± 2 weeks) after Week 48.
- ^p ECG and urinalysis will be done yearly (± 2 weeks) after Week 48 Visit.
- ^q Ultrasound will be conducted to enhance HCC surveillance. For all on study (eg, post-Day 1) ultrasounds: Unless HCC has already been confirmed by biopsy, a second confirmatory image (eg, MRI) should be obtained to confirm suspected HCC.
- ^r If an ultrasound has been done within 12 months of Screening, and a report/adequate data are available, a pretreatment ultrasound at Screening is not required.
- ^s If ultrasound for gallbladder assessment was not performed at Screening and the historic ultrasound is >12 months from Day 1, perform ultrasound.

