7.6. Close Observation

If investigational product is interrupted or discontinued as described in [Section 8.4](#), patients should be closely monitored (contacted by the site a minimum of every 2 weeks and scheduled visits every 6 weeks; if returning to the site for a scheduled visit is not feasible, use of a local lab may be permissible at the Investigator's discretion). At a minimum, the following assessments should be conducted at each study visit:

- Physical exam and thorough review of patient reported signs and symptoms,
- Liver biochemistry (including ALP, ALT, AST, GGT, total and conjugated bilirubin, creatinine, and albumin), prothrombin time (PT)/INR, serum electrolytes, and assessment of Child Pugh (only if the patient is at the study site) and MELD scores.

In addition, a trough pharmacokinetic sample for assessment of OCA serum drug levels and its major metabolites should be obtained in any patient who develops an AE that is indicative of or consistent with hepatic injury or decompensation.

The following additional monitoring procedures should be performed for events of potential hepatic injury (per FDA Guidance for Industry on Drug Induced Liver Injury) or suspected hepatic decompensation based on criteria described in [Section 7.4.1](#), [Section 7.4.2](#), and [Section 7.4.3](#). These cases need to be discussed with the Sponsor's Medical Monitor:

- Repeating liver biochemistry and function tests as described in [Section 7.4.2](#). Frequency of retesting can decrease to once a week or less if abnormalities stabilize or the study drug has been discontinued and the patient is asymptomatic, as clinically indicated.
- Obtaining a more detailed history of symptoms and prior or concurrent diseases.
- Obtaining a history of concomitant drug use (including nonprescription medications and herbal and dietary supplement preparations), alcohol use, recreational drug use, and special diets is important. Concomitant drugs with potential hepatotoxicity should be recorded and discontinued unless alternative therapies are not available. In the case of concomitant drugs potentially hepatotoxic, continued use of investigational

product should be discussed with the Sponsor's Medical Monitor. The patient may be discontinued from investigational product, if clinically appropriate.

- Obtaining a history of exposure to environmental chemical agents or herbal supplements which may be associated with liver toxicity.

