8.4. Dose Adjustment, Interruption, and Withdrawal from Investigational Product or Study

Investigational product may be temporarily decreased (eg, from 10 mg twice weekly to 5 mg twice weekly, or from 5 mg twice weekly to 5 mg once weekly) or temporarily or permanently stopped based on tolerability concerns. Investigational product may be resumed at the maintenance dose upon resolution of gastroenteritis or worsening renal function or dehydration if there is no evidence of liver injury. For rechallenge following all other dose interruptions (see Table 5), investigational product should be initiated at a lower dose and patients monitored more frequently with up-titration considered based on tolerability.

Adjustments, interruptions, discontinuation, and any rechallenge of investigational product should be implemented per the criteria outlined in Table 5. Patients that discontinue investigational product are expected to continue in the study (and follow the regular visit schedule, with the exception of PK sampling [trough PK may be required in the event of an AE consistent with hepatic injury or decompensation]) until the end of the study, but may withdraw consent at any time.

Table 5: Criteria for Dose Adjustment, Interruption, Discontinuation, and Rechallenge

DOSE ADJUSTMENT		
Criteria	Action Taken with IP	Adjustment
New Onset Severe Pruritus	Drug holiday or less frequent dosing	Return to original dose regimen if tolerated
DOSE INTERRUPTION		
Criteria	Action Taken with IP^a	Rechallenge^b
If liver biochemistries indicative of suspected hepatic injury are identified as exceeding upper threshold criteria and require immediate interruption (see Part A of Table 3) ^c	Interrupt immediately upon initial observation	Patient may be rechallenged after a minimum of 30 days if fully resolved OR stable and approved by the Medical Monitor and Investigator.
Other liver biochemistries indicative of suspected hepatic injury are outside upper threshold criteria upon repeat testing as defined in Part A of Table 3 ^d	Interrupt after confirmation by repeat testing	
Liver biochemistries indicative of potential hepatic decompensation in the absence of symptoms (see Part B of Table 3) ^e	Closely monitor until normalization or stabilization. If values continue to increase relative to the baseline value, interrupt	

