Clinical events indicative of hepatic decompensation (see Part B of Table 4)	Closely monitor until normalization or stabilization	The patient may be rechallenged after a minimum of 30 days if fully resolved OR stable and approved by the Medical Monitor and Investigator. IP should be re-initiated at a lower dose (or lower dose frequency) and titrated per Investigator discretion.
Gastroenteritis (established severe abdominal pain, vomiting, diarrhea for more than 4 days)	Interrupt	If no evidence of liver injury is detected, IP may be restarted at the same dose after resolution of intercurrent illness.
Evidence of worsening of renal function or dehydration	Interrupt	
DOSE DISCONTINUATION		
Criteria	Action Taken with IP	Rechallenge
If INR increases ≥ 2.0 in absence of clinical symptoms criteria (unless due to vitamin K deficiency) ^f	Discontinue / No Rechallenge	Discontinue IP permanently and continue to return for scheduled study visits for safety follow-up.
If total bilirubin thresholds (Part B of Table 3) are observed in the presence of clinical symptoms of cholestatic hepatitis or hepatic encephalopathy ^f		Continue to return for scheduled study visits for safety follow-up. Monitor closely for clinical outcomes according to protocol assessments.
Multi-Organ failure requiring hospitalization		
Liver transplantation		
Pregnancy		

Fully resolved = Return to baseline levels or return to within normal limits (WNL). IP = investigational product

^a If patient is unable to be evaluated promptly, study drug must be immediately interrupted.

^b Requires complete documentation of complete resolution or normal/baseline results based on laboratory parameters and symptoms.

^c Total bilirubin baseline \leq ULN and $\geq 3x$ baseline, baseline $>$ ULN and $\geq 2x$ baseline, ALT or AST $> 3x$ baseline (and $>$ ULN)

^d ALT or AST $\geq 2x$ baseline or electrolytes (sodium $<$ 130 mEq/L).

^e Total bilirubin baseline \leq ULN and 1.5 mg/dL increase from baseline OR baseline $>$ ULN and 1.0 mg/dL increase from baseline; INR $>$ 0.3 increase from baseline

^f If INR increases ≥ 2.0 in the absence of clinical symptoms or if or total bilirubin thresholds OR an INR increase from baseline of ≥ 1.5 are observed in the presence of clinical symptoms of cholestatic hepatitis or hepatic encephalopathy.

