- Assess for dose titration, if eligible (refer to [Section 7.3](#)).
- Dispense investigational product only if there is dose increase or as needed. No new investigational product bottles will be dispensed if there is only change in dosing frequency of the same dose level. Patients are expected to use up each investigational product bottle before a new bottle will be dispensed.
- Perform a urine-based β -hCG pregnancy test in females of childbearing potential.
- Obtain blood samples for
 - Serum chemistry, hematology, and coagulation
- Schedule the next visit, reiterate dosing instructions, and advise the patient:
 - NOT to take investigational product on the morning of the next visit, and
 - To bring the investigational product bottle(s) to the visit, and
 - To fast overnight (at least 8 hours) prior to the next visit. Fasting is required prior to all study visits, but water is permitted.

Patients will complete a TE/ELF (HA, P3NP and TIMP 1) and ultrasound (for HCC surveillance) assessment, every 6 months (± 2 weeks) after Week 48.

ECG and urinalysis will be done yearly (± 2 weeks) after Week 48.

9.7.13. End of Study/Early Termination/End of Treatment Procedures for Patients That Withdraw from Investigational Product or Withdraw Consent

Patients who discontinue investigational product before Week 48 are expected to continue in the study until the end of the study (EOS [when patient terminates the study]) or at the discretion of the Sponsor.

EOT (when patient discontinues investigational product)/ET procedures will be required whenever patients discontinue treatment with investigational product (Table 1, Section 9.7.11). The EOT/ET Visit (Table 1) and procedures listed below (Table 6) must be performed as close as possible to the patient's last dose of investigational product. When a patient discontinues or interrupts investigational product and continues with regularly scheduled study visits, the EOS Visit will be completed as the patient's final study visit. The actual investigational product discontinuation scenario (Table 6) will determine the sequence of the EOT/ET and EOS Visits and procedures. In some cases, the EOT/ET Visit and procedures will precede the EOS Visit; in others, the EOT/ET and EOS Visits will be combined and performed as close as possible to the patient's last dose of investigational product. EOT and EOS Visits are encouraged but at no time will a missed EOT or EOS visit be considered a protocol deviation.

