When a patient ends her/his participation in the study (eg, at a point between standard study visits) either due to early termination (ET) (withdrawal of consent) or discontinuation, an EOT/EOS Visit must be performed as near as possible to her/his last dose of investigational product and the procedures listed in Table 1 performed. The purpose of this visit is to conduct complete and/or final assessments on or as near as possible to the final day of dosing. In some cases, the patient may discontinue on the day of a scheduled study visit. In these cases, EOT/EOS Visit procedures should be performed in place of the scheduled study visit procedures. The data will be recorded as EOT/ET and EOS procedures in the eCRF.

Table 6: Early Discontinuation Scenarios

	Investigational Product	Consent	Study Visit Status	EOT Visit ^a	EOS Visit ^a
Early Termination	Discontinued	Withdrawn	No additional visits except EOT/EOS	Combined visit, completed as close as possible to last dose of investigational product.	
Treatment Discontinuation^b	Discontinued	Active	Regular Visit Schedule	Complete as close as possible to last dose of investigational product.	Complete at final study visit.
	Discontinued	Record review only	Record review only	Combined visit, completed as close as possible to last dose of investigational product.	
Sponsor Termination	Discontinued	N/A	No additional visits except EOT/EOS	Combined visit, completed as close as possible to last dose of investigational product.	
Pregnancy	Discontinued	Complete per the above scenarios - Early Termination or Treatment Discontinuation			
Lost to Follow-Up	Discontinued	LTF	None	Unable to complete due to LTF status	

EOS = end of study; EOT = end of treatment; LTF = lost to follow-up

^a Refer to Section 7.1.2, Schedule of Study Procedures for all procedures and evaluations required at the EOS and EOT Visits.

^b Includes initiation of commercially available OCA.

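### Table 1 footnote k removes a patient with a confirmed on-study pregnancy from the study, while Sections 8.4 and 9.7.13 and Table 6 stop only the drug and expect or allow her visits to go on

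*Protocol*

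**What the plan says.** Footnote k to Table 1 (Section 7.1.2) sets urine pregnancy tests for women of childbearing potential before entry and at each visit other than Week 3, with a blood test to confirm a positive. It then states: "If the confirmatory blood test is also positive, the patient may not continue in the study". It makes no distinction between a test before randomization and one during treatment.

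Other current text treats a patient who stops drug differently:

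- Section 8.4: "Patients that discontinue investigational product are expected to continue in the study", on the regular schedule but without PK sampling, until the end of the study. She may withdraw consent at any time.
- Section 9.7.13: "Patients who discontinue investigational product before Week 48 are expected to continue in the study until the end of the study". The sentence goes on to allow for the Sponsor's discretion.
- Table 6 (Section 9.7.13), Pregnancy row: product is discontinued, then "Complete per the above scenarios - Early Termination or Treatment Discontinuation". The Early Termination row shows consent as withdrawn. The Treatment Discontinuation row with active consent shows the regular visit schedule.
- Section 13.1.9: treatment stops at once, the Sponsor is told within 24 hours, and mother and neonate are followed for outcome. Section 13.2.6 likewise calls for Sponsor notification and follow-up to pregnancy outcome. Neither mentions leaving the study.
- Footnote m, in the same Table 1: "Patients who are discontinued from investigational product prior to completion of the study are encouraged to continue to follow the regular visit schedule", again without PK sampling.

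**The concern.** A site with a confirmed on-study pregnancy has two instructions that it cannot both follow. Footnote k makes exit mandatory. Section 8.4 expects the patient to stay, and Table 6 lets her stay if she consents.

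A site that acts on footnote k ends scheduled visits in a Child-Pugh B or C patient who has just come off drug. Section 13.1.8 warns that drug-induced liver injury can appear or worsen after the drug is stopped, and Section 5.5 justifies the heavier monitoring by the raised risk of decompensation. What is at stake is the safety surveillance of a single patient, not an estimate or a comparison.

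**Working it through.** The protocol states no figure on this point, so there is none to reproduce. The check is a comparison of texts, then a count of what one patient would lose.

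**Step 1. Does footnote k reach on-study pregnancies?** Yes. It names testing at visits after entry, and the Table 1 row marks tests at Weeks 6, 12, 18, 24, 30, 36 and 48 and in the extension. It cannot be read as a screening rule.

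**Step 2. What happens to a consenting patient with a confirmed on-study pregnancy?**

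| Source | Drug | Study visits |
|---|---|---|
| Table 1 footnote k | not stated | end |
| Section 8.4 | stopped | expected to continue, no PK sampling |
| Section 9.7.13 | stopped | expected to continue, or at Sponsor discretion |
| Table 6, Pregnancy row | stopped | may continue on the regular schedule |
| Sections 13.1.9 and 13.2.6 | stopped (13.1.9) | pregnancy followed; exit not mentioned |

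Only footnote k requires exit.

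**Step 3. Scheduled contact lost to Week 48 by leaving instead of staying.**

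Inputs:
- Laboratory visits after Day 1 (Table 1): Weeks 3, 6, 12, 18, 24, 30, 36, 42, 48.
- Telephone or email contacts (footnote b), every 3 weeks "between clinic visits starting at Week 9 and continuing to Week 48": Weeks 9, 15, 21, 27, 33, 39, 45, which is 7.

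Lost visits = scheduled visits later than the positive test; contacts are counted the same way.

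| Positive test at | Laboratory visits lost | Contacts lost |
|---|---|---|
| Week 6 | 7 (12, 18, 24, 30, 36, 42, 48) | 7 |
| Week 12 | 6 | 6 |
| Week 18 | 5 | 5 |
| Week 24 | 4 | 4 |
| Week 30 | 3 | 3 |
| Week 36 | 2 | 2 |
| Week 48 | 0 | 0 |

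Three items are left out. The end-of-treatment visit is planned whether she leaves or stays. The two-weekly contacts of Section 7.6 have no stated duration, and that section applies only through Section 8.4, so it is not separate evidence. The number of extension visits depends on enrolment.

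**Step 4. What remains after an exit?** Sponsor notification within 24 hours and pregnancy follow-up (13.1.9, 13.2.6); an end-of-treatment/end-of-study assessment (9.7.13), which is encouraged, although missing it is not a deviation; follow-up of liver injury already showing (13.1.8); and reporting of every SAE within 30 days of leaving, with possibly attributable SAEs reportable at any later time (13.1.7). None of these schedules liver tests in a patient who appears well.

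**The case against.** The strongest defence is that a specific pregnancy rule overrides a general expectation. Sections 8.4 and 9.7.13 speak of all patients who stop drug. Section 9.7.13 adds Sponsor discretion, and Section 8.4.1 has the same proviso. This stands in part: Section 9.7.13 sets a default and does not forbid exit. It does not settle the matter, because Table 6 has its own Pregnancy row and that row permits regular visits. Discretion used case by case is also different from a blanket rule.

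A reader might infer that Table 6 never lets a consenting pregnant patient leave. That is too strong. Table 6 and the text of Section 9.7.13 tie Early Termination to withdrawn consent, but Section 8.4.2 assigns early-termination evaluations to any early withdrawal, whatever the cause. Table 6 allows her to stay; it does not compel it. The conflict needs no more than that, since footnote k forbids it.

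A reader might also take Table 5 as a direct instruction, because it lists Pregnancy under dose discontinuation and nearby rows say to "continue to return for scheduled study visits for safety follow-up". In the available text the Pregnancy row has no follow-up wording of its own, and applying its neighbours' wording means guessing at merged cells. Table 5 is given no weight here.

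The objection on harm largely stands. With 24-hour notification, the Sponsor may well correct a wrong exit. Serious liver events shortly after exit remain reportable. Under 1:1 randomization about half of the patients are on placebo and have no drug injury to watch for.

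**Conclusion.** The inconsistency is real and lies in current text. Footnote k mandates study exit after a confirmed on-study pregnancy; Section 8.4 expects continued visits, Section 9.7.13 expects them by default, and Table 6 allows them.

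Its importance is low. About 50 patients are planned, contraception is required, pregnancy is excluded at entry, and Section 5.1 gives 40 to 70 years as the typical age at diagnosis. The protocol gives no pregnancy rate, so the expected number of cases cannot be calculated. No PK or efficacy result changes.

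The documents do not support reading this as a loss of all safety follow-up. For one affected patient the loss is scheduled surveillance for liver changes not yet apparent or not serious: at most 7 laboratory visits and 7 remote contacts to Week 48, falling to none when the test is positive at Week 48. The contact count assumes that footnote b contacts continue off drug for patients on the regular schedule; the footnote is not conditional on dosing.

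The appendices of changes offer a likely origin. Version 1 withdrew pregnant patients in the body text as well; Version 2 changed the body text to continued visits but kept the footnote sentence. This explains the conflict and is not evidence for it.

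**What to change.** Amend footnote k to separate the two cases:

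- **Before randomization:** a confirmed positive test excludes the patient.
- **On study:** a confirmed positive test requires permanent discontinuation of investigational product. Scheduled safety visits continue without PK sampling under Section 8.4 unless consent is withdrawn, and the pregnancy is followed under Section 13.1.9.

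The cost is one footnote sentence in the next amendment. No procedure is added, because the visits are already in Table 1.
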